### 9.3.4. Derived Variables

All variables to be used in the final study analyses including those that are derived from curated and extracted data, will be formally defined in the SAP. Variables derived from abstracted and extracted data will include the following:

- Age at index date.
- BMI at index date ( $\pm 30$  days).

- Geographic census region of residence.
- Weighted index of comorbid disease condition. Weighting of comorbid conditions will follow the weighting as specified in the Charlson Comorbidity Index.
- Start and end dates and start and end dose of infused anti-cancer treatments from the index date through the end of the third R/R-based line of therapy or the end of the record, whichever occurs first.
- Dose changes of all oral (if applicable), infused, or injected anti-cancer therapies from the index date through the end of the third R/R-based line of therapy or the end of the record, whichever occurs first.
- Start and end schedule of infused anti-cancer treatments from the index date through the end of the third R/R-based line of therapy or the end of the record, whichever occurs first.
- Treatment regimens, derived from oral and infused agents delivered, including start and stop dates.
- Duration of anti-cancer treatments regimens from the index date through the end of the third R/R-based line of therapy or the end of the record, whichever occurs first. Duration will be calculated as the end date of last agent within a regimen minus the start date of the corresponding regimen and will be computed during the analytics phase of the project.
- Time under observation for analysis of EFS/RFS, by line, based on start date of treatment within line and dates of R/R event or disease progression, or censoring.
- Time under observation for analysis of OS from start of the first qualifying Mylotarg-containing R/R-based line of therapy, based on start of treatment in the first qualifying line setting, and based on date of death or censoring.
- Time to best response for the first qualifying Mylotarg-containing R/R-based line of therapy from the index date through the end of the third R/R-based line of therapy or the end of the record, whichever occurs first.
- Duration of tumor response for the first qualifying Mylotarg-containing R/R-based line of therapy from the index date through the end of the third R/R-based line of therapy or the end of the record, whichever occurs first.

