### 3.4. Eligibility Criteria

#### 3.4.1. Inclusion Criteria

Patients must meet all of the following inclusion criteria to be eligible for inclusion in the study:

1. Confirmed diagnosis of AML on or after 01 December 2014 through Clinical Research Nurse (CRN) review of provider documentation of AML diagnosis in the medical record.
2. Receipt of Mylotarg at any point during first 3 R/R-based lines of therapy following initial AML diagnosis date occurring on or after 9/1/2017.
3. Age  $\geq 18$  years at initial diagnosis of AML.

There are no inclusion criteria related to minimum follow-up.

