### 3.5.2. Derived Variables

Variables derived from abstracted and extracted data will include the following:

- Age at index date (Table 1).
- BMI at index date ( $\pm 30$  days) (Table 1).
- Geographic census region of patient's residence (Table 1).
- Weighted index of comorbid disease condition. Weighting of comorbid conditions will follow the weighting as specified in the Charlson Comorbidity Index (Table 2).
- Start and end dates and start and end dose of infused anti-cancer treatments from the index date through the end of the third R/R-based line of therapy or the end of the record, whichever occurs first.
- Dose changes of all oral (if applicable), infused, or injected anti-cancer therapies from the index date through the end of the first R/R-based line of therapy or the end of the record, whichever occurs first (Table 4).
- Start and end schedule of infused anti-cancer treatments from the index date through the end of the third R/R-based line of therapy or the end of the record, whichever occurs first (Table 3-Table 5).
- Treatment regimens, derived from oral and infused agents delivered, including start and stop dates, and indication of subsequent treatment after 1L (Table 3-Table 5).
- Duration of anti-cancer treatments regimens from the index date through the end of the third R/R-based line of therapy or the end of the record, whichever occurs first. Duration will be calculated as the end date of a regimen minus the start date of the corresponding regimen and will be computed during the analytics phase of the project (Table 5).
- Time under observation for analysis of rwEFS/rwRFS, by line, based on start date of treatment within line and dates of R/R event or disease progression, or censoring (Table 5-Table 7).
- Time under observation for analysis of rwOS from start of the first qualifying Mylotarg-containing R/R-based line of therapy, based on start of treatment in the first qualifying line setting, and based on date of death or censoring (Table 8).

- Time to best response for each regimen in the first qualifying Mylotarg-containing R/R-based line of therapy from the index date through the end of the third R/R-based line of therapy or the end of the record, whichever occurs first (Table 9-Table 11, Table 14-Table 15).

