#### 4.3.2. Time to Event Analysis

Single time to event analyses will be conducted as specified under the study objectives. CCI [REDACTED]

Real-world time to event outcomes in this study will include:

- rwEFS/rwRFS for the first 3 R/R-based lines of therapy. rwEFS will be defined as the time from the treatment initiation date (for the first agent in the first regimen in the first line of Mylotarg-containing therapy) to the date of treatment failure (TF), relapse from Complete Response (CR) or better, or death from any cause, whichever comes first. TF is defined as failure to achieve CR or better following up to 3 cycles of Mylotarg. rwRFS will be defined as the time from the treatment initiation date (for the first agent in the first regimen in the first line of therapy) to the date of a relapse event, or death from any cause, whichever comes first.
- rwOS, from the first line of therapy through the end of record or death, whichever occurs first, and
- Duration of therapy across lines of therapy from the first line of therapy through the third R/R-based line of therapy.

The time origin for analysis of rwEFS/rwRFS is the start of therapy within each specific line of therapy, and the terminal event is the earlier of an R/R event or death. The time origin for analysis of rwOS is the start of therapy within the first line of therapy, and the terminal event is death. Patients who are not indicated to be deceased at last known contact (patients who are alive, or lost to follow-up) will be censored. The time origin for analysis of duration of therapy is start of Mylotarg, and the terminal event is discontinuation of that therapy.

#### 4.3.3. Methods under Objective 1

*Objective 1: To describe the demographic and clinical characteristics as outlined in the variable list below for patients diagnosed with AML who received Mylotarg in a real-world setting.*

Descriptive analysis as detailed in [Section 4.3.1](#) will be conducted for work under this objective. Demographic characteristics that will be reported will include sex, patient age, race/ethnicity, height, weight, BMI, insurance status, and region of residence closest to the index date. Clinical characteristics that will be reported will include comorbidities and comorbidity index score, ECOG score, and disease characteristics, such as stage at index date, cytogenetic testing at index date, and whether the AML diagnosis was de novo versus secondary.

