Demographic and clinical characteristics will not be stratified by a primary grouping variable.

#### 4.3.4. Methods under Objective 2

*Objective 2: To describe the treatment patterns from the diagnosis of AML through the end of the third R/R-based line of therapy.*

Analysis under this objective will include all study patients. Descriptive analysis as detailed in [Section 4.3.1](#) will be conducted for work under this objective. Treatment patterns include description of regimens within line of therapy for the first 3 R/R-based lines of systemic therapy as well as the description of sequences of regimens across the first 3 R/R-based lines of systemic therapy. Description of treatment regimens within line includes the frequency and percentage of each agent/regimen received, by regimen in sequence, by line, for the first 3 R/R-based lines of systemic therapy. In addition, the analysis will descriptively characterize the starting dose and dose changes of Mylotarg in each of the first lines of therapy.

Duration of treatment will also be descriptively analyzed across lines of therapy, starting with the first agent or regimen in the first line of therapy for the first 3 R/R-based lines of therapy.

### 4.3.5. Methods under Objective 3

*Objective 3: To describe the effectiveness outcomes of treatment of AML patients who received Mylotarg in a real-world setting*

Analysis under this objective will include all study patients. The outcomes of interest under this objective are rwEFS/rwRFS and rwOS. Time to event analysis as described in [Section 4.3.2](#) will be utilized.

The Kaplan-Meier product limit estimator will be employed to evaluate rwEFS/rwRFS and rwOS. The time origin for these analyses will be the start of the treatment in the respective line of therapy for rwEFS/rwRFS for the first 3 R/R-based lines of therapy. The time origin of rwOS analysis is the start of the earliest line of Mylotarg therapy. rwEFS/rwRFS and rwOS analyses for lines of therapy will be limited to patients who received treatment during the line of interest.

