**Table 5. Mylotarg Treatment Duration, by Line of Therapy**

Mylotarg Treatment Duration		N=xxx
First Line Therapy		
n		xx
Mean		x.x
SD		x.x
1 st Quartile		x.x
Median		x.x
3 rd Quartile		x.x
IQR		x.x
Min, Max		x.x,x.x
N=xxx		
Second Line Therapy		
n		xx
Mean		x.x
SD		x.x
1 st Quartile		x.x
Median		x.x
3 rd Quartile		x.x
IQR		x.x
Min, Max		x.x,x.x
N=xxx		
Third Line Therapy		
n		xx
Mean		x.x
SD		x.x
1 st Quartile		x.x
Median		x.x
3 rd Quartile		x.x
IQR		x.x
Min, Max		x.x,x.x

\* The time origin was the initiation of Mylotarg. The end point was the last date of gemtuzumab therapy, regardless of line of therapy (duration could continue into subsequent lines of therapy), study end date, or death, whichever came first.

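### Table 5 reports Mylotarg duration as a completed value with no censoring, although SAP 4.3.2 defines it as time to discontinuation, so patients still on treatment count as finished

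*SAP*

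**What the plan says.** - **SAP 4.3.2** names duration of therapy among its time-to-event outcomes: "The time origin for analysis of duration of therapy is start of Mylotarg, and the terminal event is discontinuation of that therapy". Protocol 9.7.2 has the same rule.
- **SAP 4.3.4**, the methods for Objective 2, is less specific: "Duration of treatment will also be descriptively analyzed across lines of therapy". Protocol 9.7.4 agrees. SAP 4.3.5 names the Kaplan-Meier estimator for rwEFS, rwRFS and rwOS, not for duration.
- **SAP Table 5** has rows, by line, for n, mean, SD, quartiles, median, IQR, minimum and maximum. Its footnote says "The time origin was the initiation of Mylotarg". It continues "The end point was the last date of gemtuzumab therapy, regardless of line of therapy", then adds the alternatives "study end date, or death, whichever came first".
- **SAP 3.5.2** points to Table 5 for this rule: "Duration will be calculated as the end date of a regimen minus the start date of the corresponding regimen". Protocol 9.3.4 has a variant: "Duration will be calculated as the end date of last agent within a regimen minus the start date of the corresponding regimen".
- **SAP 4.2** accepts three kinds of evidence of discontinuation: provider documentation, absence of further treatment with the agent in structured data, or hospice admission.
- **SAP 3.4.1**: "There are no inclusion criteria related to minimum follow-up".

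**The concern.** Reaching the end of the study is not the same as stopping the drug. Under SAP 4.3.2 a patient still on Mylotarg at the end of the record has not had the event. Under Table 5 the same patient contributes a finished duration to the mean and quartiles. Patients who started shortly before the cut-off are the most exposed, and nothing in eligibility keeps them out. What is at stake is the descriptive result for Objective 2d. It would be too short by an amount the table does not let a reader judge, because the number still on treatment is not shown.

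**Working it through.** The plan states no expected duration and no share of ongoing patients, so there is no figure to reproduce. The check has two parts.

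**1. The texts side by side**

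| Item | SAP 4.3.2 | SAP Table 5 |
|---|---|---|
| Start | first Mylotarg | first Mylotarg |
| End | discontinuation | last gemtuzumab date, study end or death |
| Ongoing at end of record | event not reached | counted as complete |
| Summary | time-to-event | mean, SD, quartiles, range |

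Tables 6 to 8 (rwEFS, rwRFS, rwOS) and Tables 11 and 12 (duration of and time to best response) all carry an events/patients row and a 95% CI for the median. Table 5 carries neither.

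A recorded infusion cannot fall after death or study end, so the footnote will normally select the last recorded infusion. An ongoing patient is then cut at that date and still treated as complete.

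**2. Possible size (illustration)**

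Assumptions, none of them from the documents except the September 2017 start: Mylotarg starts are uniform over 31 months (September 2017 to March 2020), there is one common cut-off, and time to discontinuation is exponential with mean m months.

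- Share ongoing = (m/31) × (1 − exp(−31/m)).
- For an exponential duration, the mean of the truncated value is m × (1 − share ongoing), so the mean falls by exactly that share.

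| m (months) | Share ongoing = fall in mean | Ongoing patients out of 25 |
|---|---|---|
| 1 | 1/31 = 3.2% | 0.8 |
| 3 | 3/31 = 9.7% | 2.4 |
| 6 | 0.1935 × (1 − 0.0057) = 19.2% | 4.8 |

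A simulation of 400,000 patients gave 3.2%, 9.6% and 19.2%.

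The result depends on length and shape:

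- Exponential with a mean of 7 days: 7/30.4 = 0.23 month, and 0.23/31 = 0.7% ongoing, about 0.2 of 25 patients.
- A fixed 63 days (three cycles at the SAP's assumed 21 days): 63/30.4 = 2.07 months, and 2.07/31 = 6.7% ongoing. Each such patient loses half the duration on average, so the mean falls by about 3.3%.

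A second simulation used 25 patients, an assumed exponential mean of 42 days (true median 29.1) and independent exponential censoring, with 4,000 runs:

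| Ongoing | Plain mean (days) | Plain median (days) | Kaplan-Meier median (days) |
|---|---|---|---|
| 5% | 40.0 | 28.5 | 30.3 |
| 10% | 37.8 | 27.0 | 30.4 |
| 20% | 33.6 | 24.0 | 30.4 |
| 30% | 29.4 | 20.9 | 30.4 |

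The plain summaries fall as the ongoing share rises. The Kaplan-Meier median stays level, 1.2 to 1.3 days above the true value at this sample size. In a study of 20 to 30 patients, 5% to 30% ongoing is 1 to 9 patients.

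**The case against.** **The descriptive plan.** SAP 4.3.4 calls for a descriptive analysis, protocol 9.7.1 prescribes means, SDs and medians for continuous variables, and Kaplan-Meier is named only for other outcomes. On that view Table 5 delivers what Objective 2 asks. This explains how the shell arose, and it is a reason to keep those rows. It does not remove the conflict with 4.3.2 or make an unfinished course complete, and a Kaplan-Meier median is itself descriptive. Part of 4.3.2 is redacted and may hold a general censoring rule, but Table 5 has no row in which to show its result.

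**Size.** The 19% needs an assumed mean of 6 months. The only time scale in the documents is the number of cycles for judging treatment failure, 3 in the SAP and 6 in the protocol. At 21 days each that is 63 or 126 days, shorter than 6 months, though neither is a cap on treatment. A reader might take 19% as the expected bias; it is only the upper end of an illustration. This part of the objection stands.

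**Net direction.** The same footnote lets duration run into later lines, so gaps off the drug may be counted and lengthen it. That is a separate issue. It means only the direction of the censoring error is established, not the net error in Table 5.

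**Day count.** A reader might also infer that a patient with a single infusion scores 0 days and that every duration is materially understated. The documents do not support this. The subtraction in SAP 3.5.2 is written for a regimen, while the Table 5 footnote sets its own Mylotarg dates without a day-count rule. Zero follows only from joining the two, and would not arise where companion agents run longer and the regimen dates are used. Adding a day is a convention, and neither document gives a Mylotarg infusion schedule from which to compute a percentage.

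**Conclusion.** The point holds. SAP 4.3.2 and Table 5 treat the same outcome in incompatible ways, and counting ongoing patients as finished can only shorten the reported duration for Objective 2d. The size cannot be fixed from the documents. It is roughly the ongoing share under exponential durations (3% to 19% for assumed means of 1 to 6 months), smaller if durations are more uniform, near zero if treatment is short, and zero if nobody is ongoing at the end of the record. The change is worth making even then, because Table 5 as drafted would not show that nobody was ongoing. The missing unit and day-count convention in Table 5 are a minor clarification.

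**What to change.** Reconcile SAP 4.3.2, 4.3.4 and Table 5:

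- Add to Table 5 the number of events/patients, the number ongoing, and a Kaplan-Meier median with 95% CI.
- Count as the event discontinuation as defined in SAP 4.2, or death on treatment. Censor patients with no discontinuation at the end of the record.
- State how an ongoing patient is told apart from one whose last recorded dose was the final one. SAP 4.2 can infer discontinuation from the absence of later treatment, which does not separate the two when the record ends soon after an infusion. The 63-day interval already in SAP 4.2 is one available reference.
- Keep the existing mean, SD, quartiles and range if wanted, labelled as observed duration.
- State the unit and the day-count convention.

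The cost is SAP and shell wording plus one more run of a method already in the SAP, on dates already collected. The drawback is precision: with 20 to 30 patients spread over three lines, some medians or confidence limits may not be estimable, and the table should say so where that happens.

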### 7.3. Objective 3: Effectiveness Outcomes

#### 7.3.1. rwEFS/rwRFS in the First Mylotarg-containing Line of Therapy

**Table 6. Kaplan-Meier Analysis of rwEFS from Initiation of First Mylotarg-Containing Line of Therapy, All Patients**

	N=xxx
No. of Events/No. of Patients	xxx/xxx
Median (months)	x.x
95% CI of Median	[x.x, x.x]

The time origin was the line of therapy in which Mylotarg treatment initiated.

**Table 7. Kaplan-Meier Analysis of rwRFS from Initiation of First Mylotarg-Containing Line of Therapy, All Patients**

	N=xxx
No. of Events/No. of Patients	xxx/xxx
Median (months)	x.x
95% CI of Median	[x.x, x.x]

The time origin was the line of therapy in which Mylotarg treatment initiated.

**Figure 1. Kaplan-Meier Analysis of rwEFS from Initiation of First Mylotarg-Containing Line of Therapy, All Patients**

**Figure 2. Kaplan-Meier Analysis of rwRFS from Initiation of First Mylotarg-Containing Line of Therapy, All Patients**

#### 7.3.2. rwOS from Initiation of First Mylotarg-Containing Line of Therapy

**Table 8. Kaplan-Meier Analysis of rwOS from Start of First Mylotarg-Containing Line of Therapy, All Patients**

	N=xxx
No. of Events/No. of Patients	xxx/xxx
Median (months)	x.x
95% CI of Median	[x.x, x.x]

The time origin was the line of therapy in which Mylotarg treatment initiated.

**Figure 3. Kaplan-Meier Analysis of rwOS from Start of First Mylotarg-Containing Line of Therapy, All Patients**

#### 7.4. Objective 4: Response

**Table 9. First Positive Response (First Mylotarg-Containing Line of Therapy), All Patients**

Description	L1 n=xxx	L2 n= xxx	L3 n=xxx
First Positive Response*, n (%)			
Complete Response (CR)	n (x.x%)	n (x.x%)	n (x.x%)
Partial Response (PR)	n (x.x%)	n (x.x%)	n (x.x%)
Stable Disease (SD)	n (x.x%)	n (x.x%)	n (x.x%)
Progressive Disease (PD)	n (x.x%)	n (x.x%)	n (x.x%)
Not Evaluable (NE)/Undocumented	n (x.x%)	n (x.x%)	n (x.x%)
Other Favorable	n (x.x%)	n (x.x%)	n (x.x%)
Other Unfavorable	n (x.x%)	n (x.x%)	n (x.x%)
Complete Response with Partial Hematologic Recovery (CRh) ±	n (x.x%)	n (x.x%)	n (x.x%)
Complete Response with Incomplete Hematologic Recovery (CRi) ±	n (x.x%)	n (x.x%)	n (x.x%)
Morphologic Leukemia-Free State (MLFS) ±	n (x.x%)	n (x.x%)	n (x.x%)
Overall Response Rate**±	xx (xx.x%)	xx (xx.x%)	xx (xx.x%)

\* Responses are based on treating physician's assessment as provided in the medical records.

\*\* Overall response rate is defined as a percentage of patients whose best response is either CR, CRh or CRi.

± Based on provider documentation, which may result in low sample size of patients with certain response categories.

**Table 10. Best Overall Response from Initiation of First Mylotarg-Containing Line of Therapy, All Patients**

Description	L1 n=xxx	L2 n= xxx	L3 n=xxx
Best Overall Response*, n (%)			
Complete Response (CR)	n (x.x%)	n (x.x%)	n (x.x%)
Partial Response (PR)	n (x.x%)	n (x.x%)	n (x.x%)
Stable Disease (SD)	n (x.x%)	n (x.x%)	n (x.x%)
Progressive Disease (PD)	n (x.x%)	n (x.x%)	n (x.x%)
Not Evaluable (NE)/Undocumented	n (x.x%)	n (x.x%)	n (x.x%)
Other Favorable	n (x.x%)	n (x.x%)	n (x.x%)
Other Unfavorable	n (x.x%)	n (x.x%)	n (x.x%)
Complete Response with Partial Hematologic Recovery (CRh) ±	n (x.x%)	n (x.x%)	n (x.x%)
Complete Response with Incomplete Hematologic Recovery (CRi) ±	n (x.x%)	n (x.x%)	n (x.x%)
Morphologic Leukemia-Free State (MLFS) ±	n (x.x%)	n (x.x%)	n (x.x%)
Overall Response Rate**±	xx (xx.x%)	xx (xx.x%)	xx (xx.x%)

\* Responses are based on treating physician's assessment as provided in the medical records.

\*\* Overall response rate is defined as a percentage of patients whose best response is either CR, CRh or CRi.

± Based on provider documentation, which may result in low sample size of patients with certain response categories.

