### 3.3. Study Size

CCI

Initial exploration of the Definitive Oncology Dataset suggests the study sample size will be between 20 and 30 patients. The aims of this research are descriptive. Accordingly, statistical power for inferential testing comparing effectiveness outcomes across groups is not indicated. Therefore, power calculation is not applicable.

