### 4.2. Regimens and Lines

For purposes of this study, a **regimen** will be defined as 1 or more anti-cancer agents given in combination, over a period of time, in which the following conditions hold:

1. All agents start within 30 days of the start of the first agent in the combination, unless the start of an agent later than 30 days after the start of the first agent is specifically indicated as planned at the time of the start of the first agent.
2. No agent is discontinued and replaced by another agent within 30 days of the start of the first agent in the combination.
  - a. All agents in the regimen must be discontinued for the regimen to be considered as discontinued. If only a single agent within a regimen is discontinued after 30 days, the regimen is assumed to be ongoing so long as the other agents are not yet discontinued.
3. No agent is held and then resumed after an interval of more than 63 days. A standard chemotherapy cycle is assumed to be 21 days; 63 days allows for a delay of 3 cycles of chemotherapy without a change in regimen.

Please note: These conditions do not dictate how detailed information about oncology medications is captured, or how medication start and end dates are recorded, regardless of the days' supply of any given prescription. Rather, the conditions are only used to define lines of therapy, and information about medications and days' supply is recorded as documented in the medical record.

Accordingly, unless the record indicates a planned delay in the start of an agent, the addition of a new agent to an existing therapy more than 30 days after start of the regimen constitutes a change of regimen. Holding of an agent for a brief period is not interpreted as a change of regimen. However, discontinuation and resumption of an agent after an interval of more than

63 days is interpreted as signaling a new regimen. Discontinuation of all agents in a regimen signals the end of the regimen. Occurrence of an R/R event or a disease progression does signal the end of a regimen. Continuation after R/R event or progression of a treatment being given before the R/R event or progression will be interpreted as a new regimen—albeit identical to the previous one. This scenario, treatment through progression, occurs in some settings, and is identifiable in study data with the coding rules described here.

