A discontinuation will be defined as stopping of a particular agent for any reason, as indicated by provider documentation of “discontinuation” or “change in therapy” in the medical record, or, in the absence of provider documentation of discontinuation or change in treatment, a change in treatment with a particular agent, with no further treatment with that agent documented in structured data, or, evidence that the patient is admitted to hospice care (as the assumption is made that all systemic therapy is discontinued at that time).

For purposes of this study, first line therapy will be defined as beginning with the first regimen the patient receives after diagnosis of the disease of interest. Subsequent lines in this study will be defined as *R/R-based lines*. *R/R-based lines* are defined by the occurrence of an R/R event or a disease progression - either may be cited, in which an R/R event or disease progression must occur for a new regimen to be interpreted as a new line of therapy. In this study, **refractory** AML is defined as disease that is nonresponsive or failing to achieve at least minimal response while on therapy. **Relapsed** status is defined as the recurrence or worsening of disease following achievement of at least a minimal response. Additionally, the documentation of advancement of disease in patients after initial AML diagnosis but before initial AML treatment will be interpreted as a disease progression. R/R events and disease progression will be defined based on provider documentation, which primarily includes progress notes.

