rwEFS will be defined as the time from the treatment initiation date (for the first line of Mylotarg-containing therapy) to the date of treatment failure (TF), relapse from CR or better, or death from any cause, whichever comes first. TF is defined as failure to achieve CR or better following up to 3 cycles of Mylotarg. Accordingly, the time origin for rwEFS will be the start of Mylotarg in the first line of therapy in which it is used. The terminal event for analysis of rwEFS is the earlier of treatment failure, relapse from CR or better (as evidenced by provider documentation), or death. Patients who have not died or experienced an event by the date of last contact within the medical record will be censored for analysis of rwEFS.

rwRFS will be defined as the time from the treatment initiation date (during the first line of Mylotarg-containing therapy) to the date of a relapse event, or death from any cause, whichever comes first. The time origin for rwRFS will be the start of Mylotarg in the first line of therapy in which it is used. The terminal event for analysis of rwRFS will be the earlier of a relapse event (as evidenced by provider documentation), or death. Patients who have not died or experienced a relapse event by the date of last contact within the medical record will be censored for analysis of rwRFS.

The time origin of rwOS analysis is the start of the first Mylotarg use. The terminal event for analysis of rwOS is date of death. Note that Social Security Disability Insurance (SSDI) records have an expected lag of up to 4 months. Accordingly, patients who are not indicated to be deceased in clinical records or SSDI records will be censored for rwOS analysis as of the later of 1) the latest date known alive within the clinical record, 2) 4 months prior to the date of most recent SSDI update.

Separate Kaplan-Meier analyses will be conducted for each rwEFS, rwRFS and rwOS endpoint.

#### 4.3.6. Methods under Objective 4

*Objective 4: To evaluate response among AML patients who received Mylotarg in a real-world setting.*

- a. First and best response for each regimen in the first qualifying Mylotarg-containing R/R-based line of therapy.
- b. Time to best response for each regimen in the first qualifying Mylotarg-containing R/R-based line of therapy.
- c. Duration of best response for each regimen in the first qualifying Mylotarg-containing R/R-based line of therapy.

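### The SAP does not settle whether rwEFS, rwRFS and response run from the start of the line or from first Mylotarg, so remission and event-free time before Mylotarg can be credited to it

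*SAP*

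**What the plan says.** Two rules in SAP 4.2 matter here. On regimens, "the addition of a new agent to an existing therapy more than 30 days after start of the regimen constitutes a change of regimen", unless the delay was planned. On lines, "an R/R event or disease progression must occur for a new regimen to be interpreted as a new line of therapy". One line can therefore hold several regimens, and the Table 3 shell provides for this (L1R1, L1R2). SAP 3.4.1 admits patients given Mylotarg at any point in the first three lines, so it need not be part of a line's first regimen.

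For rwEFS, SAP 4.3.2 starts the clock at the "treatment initiation date (for the first agent in the first regimen in the first line of Mylotarg-containing therapy"). The endpoint-specific text of SAP 4.3.5 says instead that "the time origin for rwEFS will be the start of Mylotarg in the first line of therapy in which it is used", and says the same for rwRFS. The Table 6 footnote returns to the line: "The time origin was the line of therapy in which Mylotarg treatment initiated". Table 7 repeats that footnote.

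For response, Objective 4 (SAP section 2) and SAP 4.3.6 ask for first response, best response, time to best response and duration by regimen within the first Mylotarg-containing line. Tables 9-12, 14 and 15 have columns only for L1, L2 and L3. Table 10 is titled "Best Overall Response from Initiation of First Mylotarg-Containing Line of Therapy, All Patients", and the footnotes to Tables 11 and 12 take the line as origin.

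**The concern.** Take a patient who reaches CR on L1R1 without Mylotarg, has no R/R event, and is then given Mylotarg in L1R2. L1 is that patient's first Mylotarg-containing line. A table built from line start counts the CR as a response in that line, although it came before the drug.

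Under a line-start origin the same patient also brings event-free time from before exposure. A relapse or progression before Mylotarg would have opened a new line, and death would have prevented exposure, so the interval up to Mylotarg cannot contain an event. This is immortal time.

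SAP 4.1 names rwEFS/rwRFS, rwOS and response as the primary endpoints. Two programmers working from this SAP could report different medians and a different ORR from the same data.

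**Working it through.** **No planned figure to reproduce.** The size is a database count ("Initial exploration of the Definitive Oncology Dataset suggests the study sample size will be between 20 and 30 patients") and the SAP adds "Therefore, power calculation is not applicable". The check is mainly a comparison of passages, followed by an illustration.

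**Time origins in the SAP, side by side**

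| Place | rwEFS | rwRFS | rwOS |
|---|---|---|---|
| 4.3.2, definitions | start of first Mylotarg-containing line | start of first line, with no mention of Mylotarg | first line |
| 4.3.2, closing paragraph | start of each line | start of each line | start of first line |
| 4.3.5, general paragraph | start of each line | start of each line | start of earliest Mylotarg line |
| 4.3.5, endpoint-specific text | start of Mylotarg | start of Mylotarg | first Mylotarg use |
| Footnotes, Tables 6, 7, 8 | line in which Mylotarg began | same | same |
| Footnote, Table 13 | start of first gemtuzumab-containing line | not shown | not shown |

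The footnotes cannot be read as shorthand for first Mylotarg: the Table 5 footnote does name the initiation of Mylotarg, so the SAP distinguishes the two dates.

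**Response.** Collection begins at the index date, which is AML diagnosis (SAP 3.5.1.1). SAP 4.3.6 defines ORR as a percentage of patients but does not say which regimen's response enters it. Assessment by regimen would not fully settle the matter either: under SAP 4.2 an agent may start up to 30 days after the first agent, or later if planned, and still belong to the same regimen.

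**Illustration, ORR.** Let q be the share already in CR at first Mylotarg and r the ORR in the rest. Both are assumed.

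Line-level ORR = q + (1 − q)r, an excess of q(1 − r) over r.

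- r = 50%: q = 10%, 20%, 30% gives 55%, 60%, 65%.
- r = 60%, the lower end of the background remission rate in SAP section 1: q = 10%, 20%, 40% gives 64%, 68%, 76%.
- r = 30%, q = 40%: 58%, an excess of 28 points.

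With 25 patients, 5 of them already in CR, and 12 responders among the other 20, the line-level result is 17/25 = 68% (Clopper-Pearson 95% CI 47-85). Leaving the 5 out gives 12/20 = 60% (36-81). Keeping them in the denominator but not counting their earlier CR gives 12/25 = 48%. In that last comparison each such patient moves ORR by 1/30 to 1/20, or 3.3 to 5 points, across the planned 20-30 patients.

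**Illustration, rwEFS.** Assume exponential rwEFS from Mylotarg start with median m, the same for early and late starters. A share f starts Mylotarg g months into the line. For t ≥ g, with λ = ln 2/m,

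S(t) = (1 − f)e^(−λt) + f·e^(−λ(t − g)).

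Setting S = 0.5 gives a line-start median of m + ln(1 − f + f·e^(λg))/λ.

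- m = 4, f = 20%: g = 1, 2, 3 gives 4.21, 4.46, 4.74 months.
- m = 6: 6.11 (f = 10%, g = 1), 6.44 (20%, 2), 7.33 (40%, 3).
- m = 12, same pairs: 12.10, 12.42, 13.26.
- f = 0: the median is m, with no bias.

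**The case against.** The strongest reply is that the SAP already holds the right rules. The endpoint-specific text of 4.3.5 sets the start of Mylotarg for rwEFS and rwRFS, and Objective 4 and 4.3.6 call for response by regimen, under which a CR on L1R1 belongs to L1R1. This stands as far as it goes. A reader might infer that the plan simply counts rwEFS and rwRFS from line start; it does not. What remains is that 4.3.2, the general paragraph of 4.3.5 and the footnotes say otherwise, and that the shells drop the regimen level without saying which regimen fills each cell.

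A second reply is that the study is descriptive and Objective 4 is framed around the Mylotarg-containing line, so line start could be the intended target. That is a legitimate choice, but it would have to be stated once, applied throughout, and labelled as the outcome of the line rather than of Mylotarg.

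Third, the size is assumed. The share of late starters could be zero, and most of the illustrated ORR shifts fall inside 95% intervals about 36-44 points wide at 20-30 patients. This is true, but for ORR, rwEFS and rwRFS the shift goes one way and a confidence interval does not reveal it.

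Three further inferences go too far:

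- **Time to best response is not bound to favour Mylotarg.** Line start lengthens it for a late starter who responds after Mylotarg, and a CR before Mylotarg can move it either way.
- **The gap before Mylotarg need not exceed 30 days.** Under the second regimen condition in SAP 4.2, replacing an agent within 30 days also breaks the regimen.
- **The line itself is not agreed.** For rwRFS, 4.3.2 names the first line without requiring Mylotarg in it. Table 9, for its part, states no origin at all.

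**Conclusion.** The concern holds as an unresolved contradiction in the time origin for rwEFS and rwRFS, with the same conflict for rwOS between the Table 8 footnote and 4.3.5, and as a missing rule that ties response to Mylotarg. These are primary endpoints, so it should be settled before the tables are run.

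Bias is conditional, not shown. It needs both the line-start wording to be followed and some patients to start Mylotarg after the line began. Given both, ORR rises if late starters were already in remission, and rwEFS and rwRFS lengthen by time in which no event could occur. The direction for time to best response is open.

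On the assumed ranges for rwEFS (f = 10-40%, g = 1-3 months), a 6- or 12-month median lengthens by about 0.1 to 1.3 months. ORR rises by 3 to 16 points when r is 60-70% and q is 10-40%, and by more when r is lower. The documents give none of these shares or gaps, so the actual size is unknown and may be nil.

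**What to change.** - **Time origin.** Use the date of first Mylotarg administration as the single origin for rwEFS, rwRFS, rwOS and time to best response in SAP 4.3.2, both parts of 4.3.5, and the footnotes to Tables 6-8, 12 and 13. Bring Objective 3b, which words rwOS from the start of the line, into agreement.
- **Duration of best response.** Correct the Table 11 footnote so that duration is not timed from line start.
- **Response.** In 4.3.6 and Tables 9-12, 14 and 15, report the Mylotarg-containing regimen and count only responses first documented after the first Mylotarg dose.
- **Late starters.** Report how many patients start Mylotarg in a later regimen. Show those already in CR, CRh or CRi at first Mylotarg in a separate row, and give ORR with and without them in the denominator, since dropping them from the only denominator is debatable. State how the treatment-failure definition applies to them, because a patient already in CR can hardly meet it under either origin.
- **Sensitivity analysis.** Keep the line-start version, labelled as such.

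The cost is mostly wording and a little programming. Treatment, R/R and response dates are already to be collected (protocol 9.3.2 and 9.3.3; SAP 3.5.1 and 4.3.6). ORR may come out lower or a median shorter. Protocol 9.7.2 and 9.7.5 also count rwEFS and rwRFS from line start, and protocol 9.7 says major changes to primary endpoint definitions would be reflected in an amendment, so the sponsor should decide whether one is needed.
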